14.3.2 Adverse Event Characteristics

- **CTCAE term (AE description) and grade:** The descriptions and grading scales found in the revised NCI Common Terminology Criteria for Adverse Events (CTCAE) version 4.0 will be utilized for AE reporting. All appropriate treatment areas should have access to a copy of the CTCAE version 4.0. A copy of the CTCAE version 4.0 can be downloaded from the CTEP web site http://ctep.cancer.gov/protocolDevelopment/electronic_applications/ctc.htm.
- **For expedited reporting purposes only:**
 - AEs for the agent that are **bold and italicized** in the CAEPR (i.e., those listed in the SPEER column, should be reported through CTEP-AERS only if the grade is above the grade provided in the SPEER.
- **Attribution** of the AE:
 - Definite – The AE is clearly related to the study treatment.
 - Probable – The AE is likely related to the study treatment.
 - Possible – The AE may be related to the study treatment.
 - Unlikely – The AE is doubtfully related to the study treatment.
 - Unrelated – The AE is clearly NOT related to the study treatment.

14.4 Expedited Adverse Event Reporting

14.4.1 Expedited AE reporting for this study must use CTEP-AERS (CTEP Adverse Event Reporting System), accessed via the CTEP Web site (<http://ctep.cancer.gov>). The reporting procedures to be followed are presented in the “NCI Guidelines for Investigators: Adverse Event Reporting Requirements for DCTD (CTEP and CIP) and DCP INDs and IDEs” which can be downloaded from the CTEP Web site (<http://ctep.cancer.gov>). These requirements are briefly outlined in the tables below

In the rare occurrence when Internet connectivity is lost, a 24-hour notification is to be made to CTEP by telephone at [contact]. Once Internet connectivity

is restored, the 24-hour notification phoned in must be entered electronically into CTEP-AERS by the original submitter at the site.

14.4.2 Expedited Reporting Guidelines

Use the NCI protocol number and the protocol-specific patient ID assigned during trial registration on all reports.

Note: A death on study requires both routine and expedited reporting regardless of causality, unless as noted below. Attribution to treatment or other cause must be provided.

Death due to progressive disease should be reported as **Grade 5 “Disease progression” in the system organ class (SOC) “General disorders and administration site conditions.”** Evidence that the death was a manifestation of underlying disease (e.g., radiological changes suggesting tumor growth or progression: clinical deterioration associated with a disease process) should be submitted.

Phase 1 and Early Phase 2 Studies: Expedited Reporting Requirements for Adverse Events that Occur on Studies under an IND/IDE within 30 Days of the Last Administration of the Investigational Agent/Intervention^{1,2}

FDA REPORTING REQUIREMENTS FOR SERIOUS ADVERSE EVENTS (21 CFR Part 312)

NOTE: Investigators **MUST** immediately report to the sponsor (NCI) **ANY** Serious Adverse Events, whether or not they are considered related to the investigational agent(s)/intervention (21 CFR 312.64)

An adverse event is considered serious if it results in **ANY** of the following outcomes:

- 1) Death
- 2) A life-threatening adverse event
- 3) An adverse event that results in inpatient hospitalization or prolongation of existing hospitalization for ≥ 24 hours
- 4) A persistent or significant incapacity or substantial disruption of the ability to conduct normal life functions
- 5) A congenital anomaly/birth defect.
- 6) Important Medical Events (IME) that may not result in death, be life threatening, or require hospitalization may be considered serious when, based upon medical judgment, they may jeopardize the patient or subject and may require medical or surgical intervention to prevent one of the outcomes listed in this definition. (FDA, 21 CFR 312.32; ICH E2A and ICH E6).

ALL SERIOUS adverse events that meet the above criteria **MUST** be immediately reported to the NCI via CTEP-AERS within the timeframes detailed in the table below.

Hospitalization	Grade 1 and Grade 2 Timeframes	Grade 3-5
------------------------	---------------------------------------	------------------

		Timeframes
Resulting in Hospitalization ≥ 24 hrs	10 Calendar Days	24-Hour 5 Calendar Days
Not resulting in Hospitalization ≥ 24 hrs	Not required	

NOTE: Protocol specific exceptions to expedited reporting of serious adverse events are found in the Specific Protocol Exceptions to Expedited Reporting (SPEER) portion of the CAEPR.
 
Expedited AE reporting timelines are defined as:
 
 ○ “24-Hour; 5 Calendar Days” - The AE must initially be reported via CTEP-AERS within 24 hours of learning of the AE, followed by a complete expedited report within 5 calendar days of the initial 24-hour report. ○ “10 Calendar Days” - A complete expedited report on the AE must be submitted within 10 calendar days of learning of the AE. 		

¹Serious adverse events that occur more than 30 days after the last administration of investigational agent/intervention and have an attribution of possible, probable, or definite require reporting as follows: Expedited 24-hour notification followed by complete report within 5 calendar days for:
 
 • All Grade 3, 4, and Grade 5 AEs 
Expedited 10 calendar day reports for:
 
 • Grade 2 AEs resulting in hospitalization or prolongation of hospitalization 
²For studies using PET or SPECT IND agents, the AE reporting period is limited to 10 radioactive half-lives, rounded UP to the nearest whole day, after the agent/intervention was last administered. Footnote “1” above applies after this reporting period.
 
Effective Date: May 5, 2011
		

14.4.3 Expedited Adverse Event Reporting for Suspected Exposure to Agent that May Cause Serious or Life-threatening Birth Defects for Patients Receiving GDC-0449

- CTEP considers **any possible prenatal exposure to GDC-0449**, a reportable expedited adverse event that should be reported to CTEP-AERS as a 24-hour notification followed by a complete report within 5 calendar days.
- Any patient suspected of being pregnant or fathering a child, (i.e. any female patient or female partner of a male patient, respectively), or should any lapse in contraception occur, should stop taking GDC-0449 until it is confirmed that pregnancy has not occurred.

- Pregnancies that occur up to 24 months after the last dose of GDC-0449 will be followed until the outcome of the pregnancy is known.
- The adverse event (pregnancy) should be reported as a Grade 4 event using CTCAE 4.0 as follows:
 - Endocrine disorders- Other (Prenatal exposure to a possible teratogen)
 - A completed “Possible Prenatal Exposure to Teratogen Report” Form ([Appendix C](#)) should be attached to the complete CTEP-AERS Report. This form may also be faxed to CTEP along with any relevant supporting medical information at [contact] (alternative [contact]).
 - This form should be submitted for any female patient or any female partner of a male patient who becomes pregnant during therapy or up to 12 months after the last dose of GDC-0449.
- Any congenital anomaly/birth defect in a child conceived to a female patient or to a female partner of a male patient exposed to GDC-0449 during treatment or within 24 months after the last dose of GDC-0449 should be reported as an expedited adverse event to CTEP-AERS as a 24-hour notification followed by a complete report within 5 calendar days.
- Abortion, whether accidental, therapeutic, or spontaneous, should always be classified as serious. Any abortion occurring during the study or within 24 months after the last dose of GDC-0449 to a female patient or to a female partner of a male patient exposed to the agent during treatment or within 24 months after the last dose of GDC-0449 should be reported as an expedited adverse event to CTEP-AERS as a 24-hour notification followed by a complete report within 5 calendar days.

14.5 Routine Adverse Event Reporting

All Adverse Events **must** be reported in routine study data submissions. **AEs reported through CTEP-AERS must also be reported in routine study data submissions.**

14.6 Secondary Malignancy

A secondary malignancy is a cancer caused by treatment for a previous malignancy (e.g., treatment with investigational agent/intervention, radiation or chemotherapy). A secondary malignancy is not considered a metastasis of the initial neoplasm.

CTEP requires all secondary malignancies that occur following treatment with an agent under an NCI IDE be reported via CTEP-AERS. Three options are available to describe the event:

- Leukemia secondary to oncology chemotherapy (e.g., acute myelocytic leukemia [AML])
- Myelodysplastic syndrome (MDS)
- Treatment-related secondary malignancy

Any malignancy possibly related to cancer treatment (including AML/MDS) should also be reported via the routine reporting mechanisms outlined in each protocol.

14.7 Second Malignancy

A second malignancy is one unrelated to the treatment of a prior malignancy (and is **NOT** a metastasis from the initial malignancy). Second malignancies require **ONLY** routine reporting via CDUS unless otherwise specified.

15 ETHICAL AND REGULATORY CONSIDERATIONS

15.1 Informed consent

Informed consent will be obtained from all research participants prior to performing any study procedures using the most recent IRB approved version.

15.2 Institutional Review

Study will be approved by the Institutional Review Board of University of Utah.

15.3 Data and Safety Monitoring Plan

A Data and Safety Monitoring Committee (DSMC) is established at Huntsman Cancer Institute (HCI) and approved by the NCI to assure the well-being of patients enrolled on Investigator Initiated Trials that do not have an outside monitoring review. Roles and responsibilities of the DSMC are set forth in the NCI approved plan. The activities of this committee include a quarterly review of adverse events including SAEs, important medical events, significant revisions or amendments to the protocol, and approval of cohort/dose escalations. If the DSMC and/or the PI have concerns about unexpected safety issues, the study will be stopped and will not be resumed until the issues are resolved. The DSMC also reviews and approves audit reports generated by the Research Compliance Office.

This study will be reviewed by the full committee at each quarterly DSMC meeting. This includes a review of all serious adverse events (SAEs) occurring in patients treated at HCI or its affiliates as well as all grade 3 or greater toxicities for patients on treatment and within 30 days follow-up window (only if possibly, probably or definitely related).

15.4 Protocol Amendments

Any amendments or administrative changes in the research protocol during the period, for which the IRB approval has already been given, will not be initiated without submission of an amendment for IRB review and approval.

These requirements for approval will in no way prevent any immediate action from being taken by the investigator in the interests of preserving the safety of all patients included in the trial.

15.5 Protocol Deviations

A protocol deviation (or violation) is any departure from the defined procedures and treatment plans as outlined in the protocol version submitted and previously approved by the IRB. Protocol deviations have the potential to place participants at risk and can also

undermine the scientific integrity of the study thus jeopardizing the justification for the research. Protocol deviations are unplanned and unintentional events.

Because some protocol deviations pose no conceivable threat to participant safety or scientific integrity, reporting is left to the discretion of the PI within the context of the guidelines below. The IRB requires the **prompt reporting** of protocol deviations which are:

- Exceptions to eligibility criteria.
- Intended to eliminate apparent immediate hazard to a research participant or
- Harmful (caused harm to participants or others, or place them at increased risk of harm - including physical, psychological, economic, or social harm), or
- Possible serious or continued noncompliance

17 APPENDIX

Refer to pages 69 – 82 for Appendices

APPENDIX A PERFORMANCE STATUS CRITERIA

ECOG Performance Status Scale		Karnofsky Performance Scale	
Grade	Descriptions	Percent	Description
0	Normal activity. Fully active, able to carry on all pre-disease performance without restriction.	100	Normal, no complaints, no evidence of disease.
		90	Able to carry on normal activity; minor signs or symptoms of disease.
1	Symptoms, but ambulatory. Restricted in physically strenuous activity, but ambulatory and able to carry out work of a light or sedentary nature (e.g. , light housework, office work).	80	Normal activity with effort; some signs or symptoms of disease.
		70	Cares for self, unable to carry on normal activity or to do active work.
2	In bed <50% of the time. Ambulatory and capable of all self-care, but unable to carry out any work activities. Up and about more than 50% of waking hours.	60	Requires occasional assistance, but is able to care for most of his/her needs.
		50	Requires considerable assistance and frequent medical care.
3	In bed >50% of the time. Capable of only limited self-care, confined to bed or chair more than 50% of waking hours.	40	Disabled, requires special care and assistance.
		30	Severely disabled, hospitalization indicated. Death not imminent.
4	100% bedridden. Completely disabled. Cannot carry on any self-care. Totally confined to bed or chair.	20	Very sick, hospitalization indicated. Death not imminent.
		10	Moribund, fatal processes progressing rapidly.
5	Dead.	0	Dead.

APPENDIX B DEFINITION OF WOMEN OF CHILDBEARING POTENTIAL AND ACCEPTABLE AND UNACCEPTABLE FORMS OF CONTRACEPTION

Women of childbearing potential are defined as follows:

- Patients with regular menses
- Patients with amenorrhea, irregular cycles, or using a contraceptive method that precludes withdrawal bleeding
- Women who have had a tubal ligation

Women are considered not to be of childbearing potential for the following reasons:

- The patient has undergone hysterectomy and/or bilateral oophorectomy.
- The patient is post-menopausal defined by amenorrhea for at least 12 months in a woman >45 years old.

Determine pregnancy status within 10-14 days prior to initiation of treatment in females of reproductive potential. For females with a negative pregnancy test, initiate a highly effective form of contraception (failure rate of less than 1%) 4 weeks prior to the first dose. Continue highly effective contraception during therapy and for 24 months after the last dose of GDC-0449

The following are acceptable forms of barrier contraception:

- Latex condom (always used with spermicide)
- Diaphragm (always used with spermicide)
- Cervical cap (always used with spermicide)

The following are acceptable forms of secondary contraception, when used with a barrier method:

- Tubal ligation
- Partner's vasectomy
- Hormonal contraception including birth control pills, patches, rings, or injections, *with the exception of the progesterone-only "mini pill"*
- Intrauterine device (non-progesterone T)
- Vaginal sponge (containing spermicide)

In addition, 100% commitment to abstinence is considered an acceptable form of contraception.

The following are **unacceptable** forms of contraception for women of childbearing potential:

- IUD progesterone T
- *Progesterone-only “mini pill”*
- Female condom
- Natural family planning (rhythm method) or breastfeeding
- Fertility awareness
- Withdrawal
- Cervical shield

APPENDIX C POSSIBLE PRENATAL EXPOSURE TO TERATOGEN REPORT

ATTACH TO CTEP-AERS 5-DAY REPORT	
Possible Prenatal Exposure to Teratogen Report	
Study #: SAE [contact] Alternate [contact]	
AdEERS Ticket Number: _____	
Initial Report Date: DD - MMM - YY	Follow-up Report Date: DD - MMM - YY
Principal Investigator:	Reporter:
Reporter Telephone #:	Reporter FAX #:
Investigator Number: [][][][][][][][] Subject Number: [][][][][][][][]	Subject Initials: [][][]
Complete all of the investigator and subject number boxes provided. Use leading zeros, when necessary, to complete all expected boxes. Example: Investigator #407 would be filled in as: [0][0][4][0][7]	
Record the first letter of the subject's first, middle and last name, in that sequence. If the subject has no middle name, enter a dash. Example: [A][-][C]	
Subject's Sex:  Female  Male	Subject's Weight: _____ kg
Subject's Date of Birth: DD - MMM - YYYY	
Subject's Ethnicity (check one only):  Hispanic or Latino  Not Hispanic or Latino  Not Available	
Subject's Race (check all that apply):  American Indian or Alaska Native  Asian  Black or African American  Native Hawaiian or Other Pacific Islander  White  Not Available	
Study Drug: GDC-0449	Study Drug Start Date: DD - MMM - YY Study Drug Stop Date: DD - MMM - YY OR  Study Drug Continuing
Dose:	Route: ORAL Frequency: QD Kit #:
First Day of Last Menstrual Period: DD - MMM - YY	Estimated Date of Delivery: DD - MMM - YY
Method of Contraception (check all that apply):  Oral Contraceptive Pills  Condoms  Periodic Abstinence  Progestin Injection or Implants  Spermicide  Diaphragm  Intrauterine Device (IUD)  Tubal Ligation  Other, specify: _____	
Reproductive History:  Gravida _____  Para _____	
Tests performed during pregnancy:  None  Unknown  CVS Results:  Normal  Abnormal  Amniocentesis Results:  Normal  Abnormal  Ultrasound Results:  Normal  Abnormal	
Pregnancy Outcome Was pregnancy interrupted?  Yes  No If yes, specify:  Elective Termination  Spontaneous Abortion  Ectopic Date of Termination: DD - MMM - YY If pregnancy was not terminated, specify pregnancy outcome (and provide infant outcome information)  Vaginal Birth:  Premature  Term OR  C-Section:  Scheduled  Emergency Date of Delivery: DD - MMM - YY Infant outcome information:  Normal  Abnormal	
Additional Case Details (if needed):	
Note: Report possible teratogen exposure to AdEERS within 24 hours. See Protocol Section 11.3.1 for instructions. Attach this form to the complete 5-day AdEERS report.	

APPENDIX D PATIENT'S MEDICATION DIARY

CTEP-assigned Protocol # _____
Local Protocol # _____

PATIENT'S MEDICATION DIARY

Today's date _____

Agent: **GDC-0449**

Patient Name _____ (initials acceptable)

Patient Study ID _____

INSTRUCTIONS TO THE PATIENT:

1. Complete one form for each cycle of treatment.
2. You will take **GDC-0449** capsules once daily. You should take the capsules at approximately the same time each day.
Dose: take ___ 150 mg capsules.
3. If you have any comments or notice any side effects, please record them in the Comments column.
4. Please bring this form and your bottles of **GDC-0449** capsules when you return for each appointment.

Day	Date	Time of dose	# of capsules taken	Comments
			150 mg	
1				
2				
3				
4				
5				
6				
7				
8				
9				
10				
11				
12				
13				
14				
15				
16				
17				
18				
19				
20				
21				
22				
23				
24				
25				
26				
27				
28				

Patient's signature _____

Protocol name: Pilot Study for the Treatment of Steroid-Refractory Sclerodermatous Chronic Graft-Versus-Host Disease (GVHD) with GDC-0449
Version Date: 05APR2019
Principal Investigator: [name]

Physician's Office will complete this section:
 
1. Date patient started protocol treatment _____
 
2. Date patient was removed from study _____
 
3. Total number of capsules taken this month _____
 
4. Physician/Nurse/Data Manager's Signature _____

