5.1.1 Administration Schedule

- GDC-0449 is an oral drug. Patients should take GDC-0449 at approximately the same time according to their dose level, with or without food. Capsules should not be opened. If a patient misses a dose, he or she should be instructed not to take or make up that dose and to resume dosing with the next scheduled dose. Missed doses should not be made up. Patients will be instructed to bring all unused capsules and their medication diary (refer to [Appendix D](#)) to each study visit for assessment of compliance.
- Patients should be warned not to share their supply of GDC-0449.

- Investigators may dispense no more than a 32-day supply of GDC-0449.
- GDC-0449 will be given orally for a total of 6 months. In patients who are responsive to therapy with acceptable toxicity, the treatment period will be extended to 12 months. The initial dose will be given at 150 mg po daily. If Grade 2 hematologic or non-hematologic toxicities attributable to the study drug are observed, three different, consecutive dose reduction levels may be utilized:
 - Level -1 (150 mg po every other day)
 - Level -2 (150 mg po every three days)
 - Level -3 (150 mg po twice a week)

All initial dose reductions will start at Level -1 and proceed to the next level if the toxicity in question persists. Dosing schedules will be dependent on what day of the week the patient starts the dose reduction level; for example, patients on Dose Level -1 with a Monday start would dose on Wednesday, Friday, Sunday, and so on.

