6.1 Dose Modifications

In the case of any Grade 2 hematologic or non-hematologic toxicity attributable to the study drug, dose reductions can be performed to up to 3 different, consecutive levels as detailed below. All initial dose reductions will start at level -1, and proceed to the immediately lower level if the toxicity in question persists for at least 1 week. Dosing

schedules will be dependent on what day of the week the patient starts the dose reduction level; for example, patients on Dose Level -1 with a Monday start would dose on Wednesday, Friday, Sunday, and so on.

Dose reduction levels are:

- Level -1 (150 mg every other day)
 - Level -2 (150 mg every three days)
 - Level -3 (150 mg twice a week)
-
- GDC-0449 will be discontinued under the following circumstance:
 - Grade 3 or 4 non-hematologic or hematologic toxicity attributable to study treatment by Common Terminology Criteria for Adverse Events (CTCAE) version 4.

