9.3 Stopping Rules/Interim Analysis

Safety was assessed after 1 cycle in the first 4 subjects to ensure that no more than one grade 3-5 drug reaction occurred and that no more than 4 of 6 subjects required a dose reduction for grade 2-4 drug reactions. At the initial dose of 150 mg daily, dose reductions to 150 mg every

other day for Grade 2 drug reactions were required. As such, the dosing schema was updated to the following:

The initial dose will be given at 150 mg po daily. If Grade 2 hematologic or non-hematologic toxicities attributable to the study drug are observed, three different, consecutive dose reduction levels may be utilized (below). All initial dose reductions will start at Level -1 and proceed to the next level if the toxicity in question persists. Dosing schedules will be dependent on what day of the week the patient starts the dose reduction level; for example, patients on Dose Level -1 with a Monday start would dose on Wednesday, Friday, Sunday, and so on.

- Level -1 (150 mg po every other day)
- Level -2 (150 mg po every three days)
- Level -3 (150 mg po twice a week)

Starting with patient 05, safety will be assessed to ensure that no more than 4 subjects (50% of the number of patients left to meet the enrollment target of 12) discontinue GDC-0449 after reducing to Level -3 due to adverse effects attributable to study drug. Safety will be reviewed monthly and at the time of each grade 3-5 reaction.

GDC-0449 will be discontinued under the following circumstance:

- If no more than 4 subjects (50% of the number of patients left to meet the enrollment target of 12) enrolled discontinue GDC-0449 after reducing to Level -3 due to adverse effects attributable to study drug.

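### The patient diary pre-prints once-daily dosing and cannot express the reduced dose levels, which differ from the starting dose only in frequency

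*Combined protocol and SAP*

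**What the plan says.** **Diary.** Appendix D instructs the patient to take "capsules once daily. You should take the capsules at approximately the same time each day". The next line reads "Dose: take ___ 150 mg capsules". There is one form per cycle ("Complete one form for each cycle of treatment"), with 28 day rows and columns for date, time, capsules taken and comments. The office section asks for the month's total of capsules taken. It does not ask for the assigned level or the expected number.

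**Dosing.** Section 5.1.1 sets the start: "The initial dose will be given at 150 mg po daily". Sections 3.1, 5.1.1, 6.1 and 9.3 then list three consecutive reductions: every other day, every three days, and finally "Level -3 (150 mg twice a week". The capsule strength and the single-capsule dose stay the same; only the interval changes. Sections 5.1.1 and 5.2.2 tie the timing of doses to the patient's dose level. The diary does not.

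**Use of the diary.** Section 5.1.1 has patients bring unused capsules and "their medication diary (refer to" Appendix D) to each study visit, so that compliance can be assessed.

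**Relevance.** Section 9.3 reports that at the starting dose, reductions to every "other day for Grade 2 drug reactions were required", and that the dosing scheme was updated for that reason. The diary pages carry the footer "Version Date: 05APR2019" and belong to the same document as the updated scheme.

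**The concern.** The diary is a written instruction that the patient takes home. For a patient on the starting dose it is correct. For a patient whose dose has been reduced it contradicts the protocol, and the form gives staff no printed place to correct it.

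Three things are at stake:

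- **The patient.** Reductions are made for toxicity attributed to the drug. Following the form restores the schedule on which that toxicity arose.
- **The step-down sequence.** Section 6.1 moves a patient down a level if the toxicity persists for at least a week. A patient still dosing daily could pass through levels that were never taken.
- **The safety count.** Section 9.3 monitors discontinuations that follow reduction to Level -3, with a threshold of 4 among the remaining 8 patients. If a patient assigned to Level -3 was in fact dosing daily, the discontinuation would be counted against a level that was not tested.

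**Working it through.** The plan gives no figure to reproduce. The check counts the scheduled doses on one diary form at each level and compares them with the number that the printed instruction implies.

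**Inputs**
- Form length: 28 rows (Appendix D).
- Capsule strength and dose: 150 mg, so one capsule per dose (Sections 5.1.1, 5.2.1, 6.1).
- Intervals: daily, every other day, every three days, twice a week (Section 6.1).
- Assumption: the first dose falls on day 1 of the form.

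**Capsules per form**
- Printed instruction: 28 × 1 = 28 (28 × 150 = 4,200 mg).
- Level -1: days 1, 3, …, 27 = 14 (2,100 mg).
- Level -2, every third day: days 1, 4, …, 28 = 10 (1,500 mg). The long-run average is 28/3 = 9.3.
- Level -2, if three days lie between doses: days 1, 5, …, 25 = 7 (1,050 mg).
- Level -3: 2 per week × 4 weeks = 8 (1,200 mg).

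The every-fourth-day reading would put Level -2 below Level -3 (7 against 8), which sits poorly with consecutive reductions. The documents do not spell the interval out, so both readings are shown.

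**Ratio (28 ÷ assigned) and apparent compliance (assigned ÷ 28)**

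| Level | Assigned | Ratio | Apparent compliance of a fully adherent patient |
|---|---|---|---|
| -1 | 14 | 28/14 = 2.0 | 14/28 = 50% |
| -2, every third day | 10 (9.3 long run) | 28/10 = 2.8 (28/9.33 = 3.0) | 10/28 = 36% (33%) |
| -2, every fourth day | 7 | 28/7 = 4.0 | 7/28 = 25% |
| -3 | 8 | 28/8 = 3.5 | 8/28 = 29% |

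The last column applies only if intake is judged against the printed daily schedule. No section instructs that.

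**Can the blank express a reduction?** No. At every level the correct entry is 1. With 1 entered, the form still directs daily intake.

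**Would supply prevent it?** Not necessarily. Section 5.2.1 gives 32 capsules per bottle, and 32 exceeds 28, so one full bottle covers a form taken daily. Section 5.1.1 caps dispensing at a 32-day supply. If that supply were counted out to the assigned level, it would be 16 capsules at Level -1, 11 at Level -2 (every third day) and about 9 at Level -3 (32 × 2/7 = 9.1), and daily intake would run out early. The documents do not say whether bottles are dispensed whole.

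**The case against.** The best reply is that the diary is not the patient's only instruction and not the only check. Sections 5.1.1 and 5.2.2 tie dosing to the level. Because the dosing days depend on the weekday on which the reduction starts, staff must explain the schedule to each patient. The diary records the date and number of capsules for each day, and unused capsules come back at visits, so actual intake can be reconstructed. Dose changes and discontinuations are also recorded as the action taken for each adverse event (Section 14.1.1).

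Much of this stands, and it rules out several stronger readings that a reader might infer:

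- **That the diary directs an overdose in absolute terms.** One capsule daily is the protocol's own starting dose. The excess is relative to the assigned reduced level.
- **That compliance will be misread.** No section defines compliance as capsules taken divided by 28, or gives any formula. The 29% figure needs staff to disregard the level they assigned.
- **That the Section 9.3 count is contaminated.** No section feeds diary data into it. An error requires that the patient follows the form over the clinic's advice, that this goes undetected, and that the patient then discontinues.
- **That the primary result is affected through the diary data.** Failure-free survival in Sections 10.1.1 and 10.2 does not use them.

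What the reply does not do is remove the printed contradiction. The text describes no step in which staff overwrite the frequency, and the list of appendices shows only one diary. The visit check comes after the fact: from month 4 (week 16) to month 6 (week 24) the minimum visits are eight weeks apart, which is two full forms, although dispensing may bring the patient in sooner.

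**Conclusion.** The point holds as a contradiction within the protocol. For any patient on a reduced level, Appendix D states a schedule that Sections 3.1, 5.1.1, 6.1 and 9.3 do not assign, and the form has no field that could state the right one. The size is 2.0 times the assigned amount at Level -1, 2.8 to 3.0 times at Level -2 (4.0 on the every-fourth-day reading) and 3.5 times at Level -3. This assumes one capsule per dose and a patient who follows the form literally.

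Reduced-level patients are not hypothetical, since Section 9.3 says that reductions had already been needed. The effects on compliance and on the attribution of discontinuations to Level -3 are foreseeable risks. How often they would occur cannot be estimated from the documents. Appendix E was not available to check, but its listed subject is drug interactions. Which schedule is clinically right is not judged here.

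**What to change.** Reconcile Appendix D with Sections 3.1, 5.1.1, 6.1 and 9.3:

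- Replace the pre-printed frequency with fields that staff complete for the patient's currently assigned level and dosing days. Issue a fresh form when the level changes.
- Add the expected number of capsules for the form to the office section, beside the number taken.
- State that compliance is assessed against the assigned level.

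No dose or clinical rule is proposed. The change covers one page and needs no new data collection from patients. Section 15.4 requires IRB review and approval for amendments and administrative changes, so notification alone would not be enough. The daily frequency pre-printed on the Appendix C exposure form can be corrected in the same amendment.
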